**Pharmacokinetic Endpoints**

- Pexidartinib: Cmax, Tmax, AUClast, AUCinf, kel, t1/2, CL/F, Vz/F and degree of plasma protein binding.
  - The following PK parameters of ZAAD-1006a will be calculated: Cmax, Tmax, AUClast, AUCinf, t1/2, degree of plasma protein binding
-

PL3397-A-U129 Protocol  
Version 2.0, 10 DEC 2019

---

and metabolite to parent ratio (MPR) for  
AUClast and AUCinf.

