#### **2.1.2. Secondary Objectives**

The secondary objectives of this study are:

- To assess the safety and tolerability of pexidartinib after a single oral dose of 200 mg in subjects with normal and moderately impaired hepatic function
- To determine the PK of ZAAD-1006a in subjects with moderate HI, compared to that in healthy subjects with normal hepatic function
- To assess protein binding of pexidartinib and ZAAD-1006a in moderate HI, compared to that in healthy subjects with normal hepatic function

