### **2.2. Study Hypothesis**

This is not a hypothesis testing study. This study will estimate the effect of moderate hepatic dysfunction on the PK of pexidartinib and ZAAD-1006a, compared to a group of healthy subjects with normal hepatic function.

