### **2.3. Study Endpoints**

#### **2.3.1. Primary Endpoints**

##### **Pharmacokinetic Endpoints**

- Pexidartinib: Plasma Cmax, Tmax, AUClast, AUCinf, Kel, t1/2, CL/F, Vz/F, and protein binding
- ZAAD-1006a: Plasma Cmax, Tmax, AUClast, AUCinf, t1/2, MPR based on AUClast and AUCinf, and protein binding

The following unbound PK parameters will be calculated for both pexidartinib and ZAAD 1006a:

- Cmax
- Tmax
- AUClast
- AUCinf

PL3397-A-U129 Protocol  
Version 2.0, 10 DEC 2019

- t1/2

And also for pexidartinib:

- CL/F
- Vz/F

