## 7. PHARMACOKINETIC/PHARMACODYNAMIC ASSESSMENTS

### 7.1. Pharmacokinetic Assessments

Blood samples (1 × 4-mL tube containing Li Heparin) will be collected for PK analysis of pexidartinib and ZAAD-1006a metabolite, at predose (within 60 min prior to dosing) and at 0.5, 1, 1.5, 2, 2.5, 3, 3.5, 4, 4.5, 5, 6, 8, 10, 12, 24, 36, 48, 72, 96, 120, 144, and 168 h post dose. Additional 10-mL samples will be collected to determine protein binding of pexidartinib and ZAAD-1006a at 2.5 and 24 h post dose.

Plasma will be harvested and analyzed for the quantification of pexidartinib using a validated liquid chromatography-tandem mass spectrometry method. The ZAAD-1006a metabolite will be analyzed using a qualified liquid chromatography-tandem mass spectrometry assay. Additional exploratory metabolite analysis may be conducted using the leftover plasma samples.

For the windows for PK blood sample collection and protein binding sample collection will follow the Daiichi Sankyo's Noncompartmental Analysis Guidelines.

**PK blood sample collection should have priority over other study assessments.** For other study assessments, in case the distribution of meals or time for study assessments coincide with the sample collection time, the sequence of events should be as follows: ECG, measurement of vital signs, blood sampling, and distribution of meals, unless stated differently. Deviations from the listed PK windows are regarded as protocol deviations. All other assessments should be completed within 30 min of the scheduled time point, the window for predose assessments can occur up to 90 min prior to dosing. Deviations from the scheduled time of all other procedures outside of 30 min will be regarded as protocol deviations.

The following PK parameters will be calculated by compartment-model-independent analysis, based on the total and unbound concentrations of pexidartinib in the plasma; Cmax, Tmax, AUClast, AUCinf, kel, t1/2, CL/F, and Vz/F. The following PK parameters will be calculated for ZAAD-1006a based on the total and unbound concentrations of ZAAD-1006a in the plasma: Cmax, Tmax, AUClast, AUCinf, and t1/2. The MPR will be determined based on total concentrations of pexidartinib and ZAAD-1006a.

PK analysis will be conducted in compliance with Daiichi Sankyo's Noncompartmental Analysis Guidelines.

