## **10. STATISTICAL METHODS**

### **10.1. General Statistical Considerations**

All PK and safety data obtained in this study will be displayed in data listings and, if appropriate, summarized using descriptive statistics. A detailed Statistical Analysis Plan (SAP) describing the methodology to be used in the final analysis will be prepared and finalized prior to the database lock. Changes to the statistical analyses will require a protocol amendment only if principal features of the protocol are changed. Any deviations from the planned statistical analyses in the protocol will be fully described in the SAP and the clinical study report.

Categorical data will be presented in contingency tables with cell frequencies and percentages for the subject population.

In general, data will be summarized for the moderate hepatic impairment group and the subjects with normal hepatic function. For point estimations of key PK parameters, 90% confidence intervals (CIs) for HI/normal hepatic function will be calculated (see Section 10.4.1).

For the data analysis, missing data will not be imputed; analyses will be performed on observed data only, unless otherwise noted.

Raw data will be presented with the exact precision with which they were collected.

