## 10.4. Statistical Analysis

### 10.4.1. Pharmacokinetic Analyses

The PK Analysis Set will be used for all PK analyses. Descriptive statistics will be presented for pexidartinib and ZAAD-1006a plasma concentrations at each evaluation time point and for all quantitative PK parameters of pexidartinib and ZAAD-1006a.

Plasma concentration-time data will be analyzed using noncompartmental methods. The following PK parameters of pexidartinib will be calculated using both total and unbound plasma concentrations: Cmax, Tmax, AUClast, AUCinf, kel, t1/2, CL/F, and Vz/F. Plasma PK parameters (Cmax, Tmax, AUClast, AUCinf, t1/2) will be calculated based on both total and unbound plasma concentrations of ZAAD-1006a.

PK parameters for pexidartinib and ZAAD-1006a will be assessed by descriptive statistics for the HI group and matching control group. The metabolite-to-parent ratio for AUClast and AUCinf for total concentrations, adjusted for molecular weight, will be determined for the HI and normal hepatic function groups.

Cmax, AUClast, and AUCinf of pexidartinib (based on total and unbound plasma concentrations) will be compared for the HI group and those of normal hepatic function. These comparisons between the HI group with the matched control group will be made using an analysis of variance model. The resulting point estimates (geometric least squares means), their ratios (HI/normal hepatic function), and 90% confidence intervals (CIs) for the ratios will be presented.

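### Comparing protein binding between the HI and normal groups is a stated objective for both analytes, but Section 10.4.1 plans no HI/normal estimate or confidence interval for it

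*Combined protocol and SAP*

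**What the plan says.** - **Objective.** Section 2.1.2, and the synopsis in similar words: "To assess protein binding of pexidartinib and ZAAD-1006a in moderate HI, compared to that in healthy subjects with normal hepatic function". The objective covers both analytes and is comparative.
- **Endpoint.** Section 2.3.1 lists binding under the primary endpoints for both analytes, for pexidartinib as "CL/F, V z /F, and protein binding". The synopsis wording is "degree of plasma protein binding". Neither says whether the variable is fraction unbound or percent bound.
- **Samples.** Section 7.1: "Additional 10-mL samples will be collected to determine protein binding of pexidartinib and ZAAD-1006a at 2.5 and 24 h post dose". The text gives no rule for combining the two values.
- **Analysis.** Section 10.4.1 gives descriptive statistics by group: "PK parameters for pexidartinib and ZAAD-1006a will be assessed by descriptive statistics for the HI group and matching control group". The ANOVA with HI/normal ratios and 90% CIs is limited to pexidartinib Cmax, AUClast and AUCinf, which "based on total and unbound plasma concentrations) will be compared for the HI group and those of normal hepatic function". Binding and fraction unbound are not mentioned in that section.
- **Framework.** Section 2.2: "This is not a hypothesis testing study". The same section says the study is to estimate the effect of moderate hepatic dysfunction on the PK of both pexidartinib and ZAAD-1006a. Section 10.1: "For point estimations of key PK parameters, 90% confidence intervals (CIs) for HI/normal hepatic function will be calculated (see Section 10.4.1".

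**The concern.** In an estimation study, a comparative objective is normally answered by an effect estimate with its uncertainty. Here the objective is to compare binding between groups, two dedicated samples per subject are drawn for it, and the analysis section stops at two sets of group summaries at best. A reader of the report would have to judge by eye whether binding differs, with 8 subjects on each side.

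The gap matters most for the metabolite. Section 1.2.2 reports that in the earlier hepatic impairment study (Child-Pugh classification) ZAAD-1006a AUC rose by up to approximately 50% and the metabolite-to-parent ratio by up to about 40%. In the present study that ratio is to be computed from total concentrations only. If ZAAD-1006a exposure again differs, how far a binding change accompanies it is a natural question, and the plan offers no HI/normal estimate for it.

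The unspecified scale adds a smaller problem. Summaries of percent bound and of fraction unbound can give quite different impressions of the same change, depending on how highly the analyte is bound.

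**Working it through.** The plan states no precision or power figure to reproduce. Section 10.5 gives 8 + 8 = 16 subjects and says the number has no statistical basis.

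**1. What each analyte gets under Section 10.4.1**

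| Quantity | Pexidartinib | ZAAD-1006a |
|---|---|---|
| Total Cmax, AUClast, AUCinf | HI/normal ratio, 90% CI | descriptive only |
| Unbound Cmax, AUClast, AUCinf | HI/normal ratio, 90% CI | descriptive only |
| Protein binding | not named; descriptive at most | not named; descriptive at most |

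**2. What the pexidartinib ratios imply about binding**

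Suppose each subject's unbound exposure is fraction unbound (fu) times total exposure, with the same subjects in both analyses. Then log(unbound AUC) = log(fu) + log(total AUC), so

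fu ratio = (unbound HI/normal ratio) / (total HI/normal ratio).

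This gives a point estimate. It does not give a CI, because

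Var(log fu) = Var(log unbound AUC) + Var(log total AUC) − 2 Cov(log unbound AUC, log total AUC),

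and the covariance cannot be recovered from two separate CIs. To illustrate, assume both AUCs have a CV of 40%, so each CI is the ratio ×/÷ 1.404 (step 3). The log half-width for fu can then lie anywhere from 0 to the sum of the two, that is from ×/÷ 1 up to ×/÷ 1.404 × 1.404 = 1.97.

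**3. Precision of a direct fu ratio at 8 versus 8**

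Inputs: 8 per group (Section 10.5); 90% two-sided CI (Section 10.1); one fu value per subject; 14 degrees of freedom, t(0.95, 14) = 1.761. The documents give no between-subject CV for fu, so a range is assumed.

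Factor = exp(t × σ × √(2/8)), with σ = √ln(1 + CV²) and √(2/8) = 0.5.

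| Assumed CV | σ | 90% CI factor | Interval if the estimated ratio is 2.0 |
|---|---|---|---|
| 20% | 0.198 | 1.19 | 1.68 to 2.38 |
| 30% | 0.294 | 1.30 | 1.54 to 2.59 |
| 40% | 0.385 | 1.40 | 1.42 to 2.81 |
| 50% | 0.472 | 1.52 | 1.32 to 3.03 |

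In 20,000 simulated trials with a true doubling of fu from 1%, the 90% CI for the log-fu ratio excluded 1 in 99.8% at CV 30% and in 87.6% at CV 50%.

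**4. Why the scale should be named**

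Percent bound = 100 × (1 − fu). The documents give no binding level, so this too is a range. Doubling fu moves percent bound from 90 to 80 (10 points), 95 to 90 (5 points), 99 to 98 (1 point) or 99.5 to 99.0 (0.5 point); the fu ratio is 2.0 throughout. The information is not lost on the percent-bound scale. In the same simulation at CV 30%, a CI for the difference in percent bound excluded 0 in 99.7% of trials. What can mislead is a rounded mean, or a ratio of percent bound, which had a median of 0.99 in those trials.

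**The case against.** The best defence is that the plan already covers what matters most for the parent drug. Unbound Cmax and AUC of pexidartinib get HI/normal ratios with 90% CIs, and free exposure is more directly useful than a binding ratio. This stands. A reader might infer that doubled free pexidartinib could pass as no change, and the documents do not support that: it would appear in the unbound ratios. For the parent, the only thing missing is a CI on the change in binding itself.

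Second, this is not a hypothesis-testing study, CIs are reserved for key PK parameters, and side-by-side summaries are a recognised way to assess a secondary objective with 8 per group. It is fair that binding, as a listed PK endpoint, would probably be summarised. Still, summaries give neither the HI/normal effect nor its uncertainty, and Section 2.2 commits the study to estimating effects for both analytes.

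Third, ZAAD-1006a lacks an HI/normal ratio for every parameter, so its gap is not peculiar to binding. That is correct. Binding is nonetheless the subject of its own comparative objective, and the metabolite's case is the clearest.

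Fourth, Sections 10.1 and 10.6 defer detail to a SAP to be finalised before database lock, and Section 7.1 defers to the sponsor's noncompartmental guidelines. Neither text is available here. Either may close the gap, but nothing in the text reviewed commits to it.

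**Conclusion.** The point holds as a gap that is almost free to close, not as an error in a planned result. The binding comparison has no planned HI/normal estimate or CI. For pexidartinib an indirect point estimate is available without a CI, provided unbound values are fu times total in the same subjects. For ZAAD-1006a there is no ratio at all. A direct estimate is feasible at the planned size, with a 90% CI factor of about 1.19 to 1.52. That range rests on assumed CVs of 20% to 50%, one value per subject and all 16 subjects contributing.

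Three further readings are tempting but unsupported:

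- That the plan fixes percent bound as the scale. The synopsis speaks of degree of binding and the body only of protein binding, so the scale is unspecified.
- That a doubled free fraction equals the doubled exposure assumed in Section 3.2. That assumption concerns exposure and supports the choice of dose; it says nothing about fraction unbound, and a change in free fraction need not produce an equal change in exposure.
- That the earlier study showed only total exposure to be unaffected. The protocol says exposure or PK was unaffected, without that qualifier.

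**What to change.** In Section 10.4.1, or in the SAP that implements it:

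1. Name fraction unbound as the protein-binding variable for both pexidartinib and ZAAD-1006a.
2. State how the 2.5 h and 24 h values are used: either analyse each time point separately, or use the per-subject mean of the two log values.
3. Analyse log fraction unbound with the same ANOVA as the exposure parameters, and report the HI/normal geometric mean ratio with 90% CI for each analyte.

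Percent bound can still be listed for information. The cost is a few lines of SAP wording and one added table. The samples are already scheduled, and no subjects, blood draws or procedures are added.

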This is a Phase 1, open-label, single dose PK study in male and female subjects with normal and moderately impaired hepatic function. The study will consist of 8 subjects with moderate HI and matched controls (8 healthy subjects with normal hepatic function). The severity of HI will be assessed by the NCI-ODWG criteria to identify subjects with moderate HI for enrollment in this study. The cohort of subjects with normal hepatic function will be group matched to subjects with moderate HI according to sex, age ( $\pm 10$  years [y]), and weight ( $\pm 20\%$ ) based on mean values. Subjects with moderate HI will be recruited first. Healthy subjects with normal hepatic function will be enrolled after all moderate HI subjects have received study drug.

Subjects will be screened within 21 days (d) prior to the administration of study drug. Subjects will be admitted to the clinical unit on Day -2 and will remain domiciled until the completion of all study procedures approximately 168 hours (h) after oral administration of 200 mg pexidartinib (1  $\times$  200-mg capsule). Study drug will be administered on Day 1 in the morning following an overnight fast of 10 h. Water consumption will be restricted from 1 h predose to 2 h post dose, except for the specified amount that is to be administered with study drug. Fasting will continue until 4 h after study drug administration.

Serial blood samples will be collected for PK analysis of pexidartinib and ZAAD-1006a at predose (within 30 minutes [min] prior to dosing) and at 0.5, 1, 1.5, 2, 2.5, 3, 3.5, 4, 4.5, 5, 6, 8, 10, 12, 24, 36, 48, 72, 96, 120, 144, and 168 h post dose.

Plasma will be harvested and analyzed for the quantification of pexidartinib using a validated liquid chromatography-tandem mass spectrometry method. ZAAD-1006a will be analyzed using a qualified liquid chromatography-tandem mass spectrometry assay.

---

PL3397-A-U129 Protocol  
Version 2.0, 10 DEC 2019

---

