**Statistical Analyses:** **Pharmacokinetics:**  
Descriptive statistics by population (moderate HI and healthy subjects with normal hepatic function) will be presented for pexidartinib and ZAAD-1006a plasma concentrations at each time point and for all PK parameters of pexidartinib and ZAAD-1006a for both total and unbound plasma concentrations.  
Cmax, AUClast, and AUCinf of pexidartinib (based on total and unbound concentrations) will be compared between subjects in the HI group and subjects in the matched control group with normal hepatic function. These comparisons will be made using an analysis of variance model. The resulting point estimates (geometric least squares means), their ratios (HI/normal hepatic function), and 90% confidence intervals (CIs) for the ratios will be presented.  

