## **3.2. Discussion of Study Design**

The purpose of this study is to assess the effect of moderate HI on the PK of pexidartinib. The study will consist of 8 subjects with moderate HI and 8 matched controls. The severity of HI will be assessed by the NCI-ODWG group TBIL >1.5 to 3x ULN, not due to Gilbert's syndrome. Subjects with normal hepatic function will be matched to subjects with moderate HI according to sex, age ( $\pm 10$  years [y]), and weight ( $\pm 20\%$ ) based on mean values. Subjects with HI will be recruited first. Healthy subjects with normal liver function will be enrolled after all subjects with moderate HI have received study drug.

A single 200-mg dose of pexidartinib (1  $\times$  200-mg capsule) was chosen based on the safety profile and with an assumption that moderate hepatic impairment may double the exposure. The open-label, single dose study design is appropriate for this Phase 1 study.

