### **10.2. Analysis Sets**

#### **10.2.1. Pharmacokinetic Analysis Set**

The PK Analysis Set will include all subjects who received a dose of pexidartinib and have sufficient plasma concentration data to characterize the PK parameters. The impact of clinically relevant events that may affect the estimate of PK parameters will be assessed while analyzing data and handled appropriately. Any exclusion will be clearly delineated in the report.

Individual plasma concentrations of pexidartinib and ZAAD-1006a will be reported for all subjects.

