### **10.3. Study Population Data**

The safety subject population will be summarized for demographic characteristics. Continuous demographic variables (age [calculated from the date of birth to the date when the ICF was signed], body weight, height, and BMI) for all subjects will be summarized with descriptive statistics for both groups. Categorical demographic variables (sex, race, and ethnicity) will be summarized with frequency counts and corresponding percentages.

Medical history data, physical examination data, and prior/concomitant medications will be listed.

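### Does Section 10.4.1 need to name the ANOVA terms and add a weight- and age-adjusted analysis, given that controls are matched only on group means?

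*Combined protocol and SAP*

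**What the plan says.** Section 10.4.1 compares Cmax, AUClast and AUCinf of pexidartinib, total and unbound, between the two groups: "These comparisons between the HI group with the matched control group will be made using an analysis of variance model". The Protocol Synopsis is equally short: "These comparisons will be made using an analysis of variance model". Both ask for geometric least squares means, HI/normal ratios and 90% confidence intervals. Neither lists factors or covariates, and neither mentions an adjusted or sensitivity analysis.

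On matching, the Synopsis says "The cohort of subjects with normal hepatic function will be group matched to subjects with moderate HI according to sex, age" and Section 3.2 says "Subjects with normal hepatic function will be matched to subjects with moderate HI according to sex, age". Both add tolerances of 10 years for age and 20% for weight, tied to mean values. There are 8 subjects per group, and Section 10.5 says this number has no statistical basis.

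The aim is estimation. Section 2.2 states: "This study will estimate the effect of moderate hepatic dysfunction on the PK of pexidartinib and ZAAD-1006a". Section 10.1 promises an SAP "describing the methodology to be used in the final analysis will be prepared and finalized prior to the database lock". Section 10.3 says "The safety subject population will be summarized for demographic characteristics", whereas the ratios use the PK Analysis Set, whose members must "have sufficient plasma concentration data to characterize the PK parameters" (Section 10.2.1).

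**The concern.** The HI/normal ratios are the study's main comparative result, and Section 1.3 expects them to inform dose recommendations. If the model is not fixed, two analysts could fit different terms and report different ratios from the same 16 subjects. Matching on means makes this more than a formality. If body weight affects clearance, a compliant gap in mean weight biases an unadjusted ratio; if it does not, adjusting for a gap costs precision. The study is open-label and the SAP is due only before database lock, so the choice could in principle be made after the imbalance is known.

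The demographic summary is also defined on the safety population, which may be larger than the set behind the ratios, so balance in the analysed subjects might not be shown directly.

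**Working it through.** **No figure to reproduce.** The plan gives no CV, power or margin, so the check asks how the plain reading of the model behaves.

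**Inputs from the documents:** 8 v 8; 90% interval; tolerances of ±20% in mean weight and ±10 years in mean age.

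**Assumed, not in the documents:** CV 20-50%; AUC proportional to weight^-b with b from 0 to 1; within-group SD 0.20 for log weight and 10 years for age; no age effect; true ratio 1.0.

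**1. Width of the plain model.** With s = sqrt(ln(1+CV²)) and 14 degrees of freedom, the 90% interval is the ratio divided and multiplied by exp(1.761 × s × sqrt(2/8)). At CV 30%, s = 0.2936 and the factor is exp(1.761 × 0.2936 × 0.5) = 1.30. At CV 40% and 50% it is 1.40 and 1.52.

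**2. Worst-case bias.** The ratio is multiplied by (control mean weight / HI mean weight)^b. At the limits, 1.2^0.75 = 1.147 and 0.8^0.75 = 0.846; with b = 1 the multipliers are 1.20 and 0.80. Simulated coverage at CV 30%, controls lighter / heavier, is 77% / 82% for b = 0.75 and 70% / 78% for b = 1. A non-central t calculation that treats the CV as all the within-group variation is harsher: 71% / 77% and 58% / 68%. At a 10% weight gap, simulated coverage is back to 89-91%.

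**3. Average over permitted gaps.** With gaps uniform over ±20% and ±10 years, group-only coverage is 87-90% in all 20 CV-by-b scenarios. A weight SD of 0.15 gives 82-90%; an SD of 0.25 gives 90-91%.

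**4. Would adjustment do better?** Root mean squared error of the log ratio, same gaps:

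| CV | b | Group only | Adjusted for log weight and age |
|---|---|---|---|
| 30% | 0 | 0.147 | 0.163 |
| 30% | 0.5 | 0.159 | 0.164 |
| 30% | 0.75 | 0.172 | 0.165 |
| 30% | 1 | 0.189 | 0.164 |
| 50% | 0.75 | 0.252 | 0.263 |
| 50% | 1 | 0.264 | 0.263 |

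Over all 20 scenarios group-only is lower in 13, adjusted in 6, with 1 tie. If neither covariate matters (CV 30%), the adjusted log half-width is 0.256 against 0.254 in balanced groups, but 0.330-0.344 with both gaps at the limit: 0.330/0.254 = 1.30 and 0.344/0.254 = 1.35, so 30-35% wider.

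**5. Effect of choosing between models.** With b = 0 and CV 30%, the two ratios differ by a median of 1.04-fold and by more than 10% in 16% of trials (34% at CV 50%). Always reporting the estimate further from 1 would still give about 87% coverage when b = 0, and somewhat less with a strong weight effect.

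**6. The other reading of the tolerance.** If each control must lie within 20% of the HI mean, and control weights are uniform in that window, the SD of the mean gap is (20%/√3)/√8 = 4.1%. A gap above 10% then arises in about 1% of trials.

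**7. Safety set against PK set.** Losing one of 8 subjects who lies 2 SD from the mean moves that mean by 2 SD/7: 5.7% in weight (SD 20%) or 2.9 years in age (SD 10).

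**The case for a change.** The best case for acting is that the text really does not list the terms. Least squares means fit an adjusted model as well as a plain one, and an open-label study leaves time to choose. The choice shows in the result: at CV 30% with b = 0.75, the two models differ by more than 10% in 38% of trials. One sentence would close the point, and weight, age and sex are already collected.

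The facts stand; the need for a change does not. Continuous weight and age terms would make the model an analysis of covariance, which the plan does not call for. Only categorical terms such as sex or site are not expressly ruled out. The SAP is the place for the term list, and no SAP text is among the documents, so the list cannot be called absent from the plan. An added sensitivity analysis would yield six more ratios from a model that is often noisier, and any threshold for discussing them would have no source in the documents.

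The mismatch of analysis sets is real but slight. Dosing is a single supervised inpatient dose, exclusions must be reported, and balance among 16 subjects can be checked from the listings.

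**Conclusion.** No change to the plan follows. The missing term list is a gap that analysts fill sensibly: the wording leads to a log-scale model with hepatic group as the only term. That model keeps its 90% interval at 87-90% coverage when averaged over the permitted gaps under the base assumptions, and more often than not it is the more accurate of the two models. Naming the term in the SAP would be harmless but would correct no error, and no figure or conclusion in the plan would move.

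The serious case, a 15-20% shift with coverage well below nominal, needs a mean weight gap at the 20% limit together with b of 0.75-1. The documents give no weight effect at all. Even that shift is small against the doubling of exposure that Section 3.2 assumes when choosing the dose. The conclusion rests on the assumed CVs, weight exponents and covariate SDs, and the simulation covers AUC only. A strong weight effect combined with a low CV would favour adjustment, but nothing in the documents points to that combination.
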